### **5.3 Concomitant Interventions**

#### **5.3.1 Allowed Interventions**

As individuals will not be diabetic or have severe hyperglycemia, there is no suggested rescue therapy for glucose. Subjects will be allowed to be on medications such as ACE inhibitors, statins and other blood pressure medications if they have been administered in a stable dosage during the preceding 6 months and dosage will continue unchanged during the study.

Over the counter medications taken as PRN such as Tylenol, antacids, aspirin are acceptable if not taken more than twice weekly. The use of stool softeners is acceptable. Use of bulking agents, if required, should remain constant.

#### **5.3.2 Required Interventions**

The only required intervention will be the study medication, soy-protein isolate Russian tarragon (*Artemisia dracunculus* L.) complex (5011-Nutrasorb).

#### **5.3.3 Prohibited Interventions**

Subjects who are on concomitant therapy with glucocorticoids (except topical or inhalant glucocorticoids) will not be included. Subjects who are currently on thiazolidinediones (rosiglitazone or pioglitazone) or who have taken these agents in the previous 12 weeks or on medications known to affect glucose metabolism, i.e. metformin, will not be allowed. Subjects who have chronic use of laxatives or cathartics will not be enrolled.

### **5.4 Adherence Assessment**

*Assessing Botanical Levels/Compliance:* Levels of the bioactive components will be assessed by determining concentrations of the component in blood plasma (circulating levels) and urine (excretion) on inpatient clamp days. Subjects will be given their randomized intervention (5011-Nutrasorb or placebo) two hours prior to start of OGTT (0 hour) and will have plasma obtained at 0, 30 minutes, 1, 2, 3, and 4 hours post ingestion. For the SAD study, additional plasma will be obtained at 12 and 24 hours post ingestion. After initial void, urine will be collected over a 6 hour interval. These specimens will be measured in the Botanical Core lab.

## **6. STUDY PROCEDURES**

See **Figures 1 and 2** for this information

### **6.1 Schedule of Evaluations (SEE FIGURE 1, page 13 and FIGURE 2, page 16)**

## 6.2 Description of Evaluations

### Specific Methods:

**Glucose Tolerance:** A 75-g oral glucose tolerance test will be used for screening and to assess for glucose tolerance and insulin secretory function in human studies according to the guidelines of the American Diabetes Association. Time points for assessment will include -15, 0, 30, 60, 90, 120, and 180 minutes.

### Insulin Resistance and Insulin Secretion:

#### Calculations to assess insulin resistance and insulin secretion:

Insulin sensitivity: Insulin sensitivity has been identified as a primary clinical parameter for which PMI-5011 has an effect. We will estimate insulin sensitivity by the homeostasis assessment model of insulin resistance (HOMA-IR). HOMA-IR will be calculated by the formula  $HOMA-IR = \text{fasting insulin } (\mu\text{U/ml}) \times \text{fasting glucose } (\text{mmol/l}) / 22.5$ .

Insulin secretion: Insulin secretion will be estimated by the homeostasis assessment model of  $\beta$ -cell function and the insulinogenic index. HOMA  $\beta$ -cell will be calculated by the formula  $HOMA \beta\text{-cell} = [20 \times \text{fasting insulin } (\mu\text{U/ml})] / [\text{fasting glucose } (\text{mmol/l})]$ . The insulinogenic index (a measure of insulin secretory capacity) will be defined as the ratio of the increment of insulin to the increment of glucose during the first 30 minutes after an oral glucose load is administered.

[figure not shown]
**Fasting Lipid Profile:** Subjects will be evaluated with fasting lipid profile to assess potential changes in lipid parameters including triglycerides, LDL and HDL levels.

**Body Composition:** Fat-free mass, fat mass and body fat % will be measured by dual-energy X-ray absorptiometry (DEXA).

**Plasma Bioactives:** Selective ion monitoring using the molecular masses for the bioactive compounds will be used to determine the relative abundance in the plasma and urine derived from the consumption of the extract. Amounts of bioactives will be calculated from their respective peak areas and normalized with the use of internal standards added before the chromatography.

Proposed Bioactives to be assessed: From a series of studies conducted by our group, 5 bioactive compounds were identified from PMI-5011 using *in vitro* activity guided fractionation. As with all botanical preparations, the identification of bioactive compounds does not preclude the presence of additional bioactive compounds that have not been isolated. DMC-2 was identified as the most universally active compound since it was active in all *in vitro* assays and is considered the marker compound for the extract. DMC-2 was also chemically synthesized and validated as active *in vivo*, using an acute hypoglycemic assay in mice. The bioactive compounds identified from the extract were also identified from the plasma of animals treated with PMI-5011 as shown in **Figure 3** below published by Ribnicky. The identification of the compounds requires hydrolysis treatment of the plasma using  $\beta$  glucuronidase in order to detect them, suggesting that they are present in the plasma as glucuronide conjugates, a common

metabolic form of many botanical compounds and drugs. The compounds were present in the plasma over a 6 h period. The compounds could never be detected at 24 h (data not shown).

**Figure 3.** Relative abundance of the active compounds of PMI-5011 as measured by LC-MS in the blood plasma of C57 mice treated with Pure DMC-2 (2', 4'-dihydroxy-4-methoxydihydrochalcone) formulated with 66% Labrasol or PMI-5011 formulated with 66% Labrasol over a 6 h period. DMC-2, Demethcap (6-demethoxycapillarison), DMC-1 (2', 4-dihydroxy-4'-methoxydihydrochalcone) and sakuranetin are components of PMI-5011.

In a recent study that is currently being submitted for publication by Ribnicky et al., the glucuronide conjugate of DMC-2 was identified in unhydrolyzed plasma from mice treated with the pure DMC-2. This prepublication is based on studies using 5011-Nutrasorb, which is the preparation of the Artemisia that will be used in present clinical study. The results of the studies showed that Nutrasorb-5011 has improved bioaccessibility characteristics using the TIM-1 digestive unit, improved bioavailability using hydrolyzed plasma levels of DMC-2 and improved bioactivity based on glucose measurements in mice. DMC-2 was also synthesized in gram quantities for use as a chemical standard in current and future studies.

In the present clinical study, bioavailability and pharmacokinetic data will be collected from plasma samples obtained from subjects (see treatment schedule) using the protocols described above. DMC-2 will be specifically quantified by LC-MS from hydrolyzed plasma samples based on a standard curve for DMC-2. An internal standard (to be determined) will be used to adjust for recovery. The other active compounds (see figure above) will also be analyzed by LC-MS relative to the DMC-2 because no chemical standards are available for the other compounds. Analysis of the unhydrolyzed plasma will be performed, as described for the mice treated with pure DMC-2, in order to determine if the DMC-2 in the plasma of clinical subjects is also glucuronidated. The plasma conjugate, however, may not be detectable from treatments with the PMI-5011 preparations having low levels of DMC-2 as it is not detectable in mice. Since the compounds were detectable in plasma hydrolyzed with glucuronidase in the previous clinical study, they are likely to be present in the plasma as glucuronides.

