**Figure 1: Proposed Study Design Assessing Ascending Single Dose for each period in Table 1**

a OGTT will be conducted as described in Section 6.2 and will include assessment of insulin and glucose at -15 and 0 timepoints prior to ingestion of oral glucose load and at 30, 60, 90, 120 and 180 minutes post glucose load.

b Indicates insulin and glucose assessments conducted in addition to assessments as part of the OGTT

Parameters assessed as part of SAD study will consist of assessing safety with biochemical measures, and effect on insulin action (with use of HOMA-IR), and use of insulin response to glucose as assessed during oral glucose tolerance testing (OGTT) and with HOMA- $\square$ . The OGTT will be obtained at two time points, specifically at Day -3 (prior to randomization) and at Day 1. The protocol for OGTT in regard to timing of dosing of study intervention and for insulin/glucose assessments are summarized below;

- 1) **Day -3:** OGTT will be conducted according to the specific method as outlined in Section 6.2, entitled "Glucose Tolerance". Specifically, a 75-g oral glucose tolerance test will be used to assess for glucose tolerance and insulin secretory function according to the guidelines of the American Diabetes Association. Time points for assessment of insulin glucose will be at -15, 0, 30, 60, 90, 120, and 180 minutes.
- 2) **Day 1:** The subject will be given either the placebo or specified dose of the study intervention two hours prior to the OGTT. This time point on the figure is termed "-2 hours" and specified as "Hour of OGTT".

- 3) **Day 1:** At 1 hour and 45 minutes post study intervention dosing on Day 1 (corresponding to time point -15 minutes of the OGTT) and at two hours post study intervention dosing (corresponding to 0 time point of the OGTT), insulin and glucose levels will be obtained in the fasting state and will represent baseline labs for the OGTT. After obtaining the 0 time point baseline labs of the OGTT, 75 grams of oral glucose will be ingested. Repeat insulin and glucose levels will be obtained at 30, 60, 90, 120 and 180 minutes after glucose ingestion.
- 4) **Day 1:** To evaluate effect of extract dosing on insulin/glucose over time, repeat insulin and glucose level will be evaluated at 12 hours after the start of the OGTT. These levels are outlined in Figure 1

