#### **Study Design of Multiple Ascending Dose**

**Subjects:** We will test safety, tolerability and metabolism in individuals with a wide range of BMIs representing lean, overweight and obese subjects.

**Design:** After meeting inclusion and exclusion criteria, subjects will be randomized by the study statistician to one of the treatment sequences within each subject's appropriate BMI stratum. Participants will be randomly assigned to treatment sequences as this design balances order of treatment consumption with respect to the distribution of extraneous factors, known or unknown, that may potentially confound the association and assessment of botanical supplement use and insulin sensitivity. After baseline evaluation, subjects will have an OGTT, insulin/glucose and effect on insulin action and response on Day -3. They will also have a baseline DXA. There will be three (3) study periods each evaluating exposure through 21 days (see **Figure 2**). At day 1, of each treatment period, subjects will be randomly assigned to treatment sequence based on the dosing scheme proposed in Table 2. Repeat insulin/glucose, safety labs, OGTT and fasting lipid profile will be assessed at 7, 14, and 21 days. Parameters assessed will consist of assessing safety with biochemical measures, bioactive metabolites and effect on insulin action (with use of HOMA-IR) and insulin response to glucose as assessed during OGTT and with use of HOMA- $\beta$ . Fasting lipids will be obtained at 7, 14 and 21 days of each treatment period. **Figure 2** outlines the schedule plan for metabolic testing in our multiple dose studies. We do not feel we need to alter any testing based on hormone/menstrual cycle issues that need to be timed, monitored, or controlled for with respect to the study outcomes.

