A sample of 27 subjects (3 subjects in each of 3 treatment sequences in each of 3 cohorts) will be enrolled in the multiple oral dose evaluation. Thus, all 9 subjects in Cohort 1 will be receive the placebo and both dose 1 and dose 2 of the extract; similarly, all 9 subjects in Cohort 2 will receive the placebo and both dose 2 and dose 3 of the extract; and all 9 of the subjects in Cohort 3 will receive both dose 1 and dose 3 of the extract. Randomization for the multiple dose evaluation will be carried out within each weight stratum so that each cohort once completed will have one normal weight, one overweight, and one obese subject will be assigned to each sequence. Specifically, the 9 subjects in each cohort will be enrolled with 3 subjects in each of 3 strata (normal weight – BMI =18.5-24.9 kg/m^2; overweight -- BMI = 25.0-29.9 kg/m^2; obese – BMI = 30.0-40.0 kg/m^2). The randomization will be carried out within each weight stratum so that one normal weight, one overweight, and one obese subject will be assigned to each sequence

Both randomizations will be performed using computer generated pseudo-random number generators. Because each subject receives each treatment in both studies, among treatment comparisons will be made using within-subject data. Thus, the main purpose of stratifying treatment assignment by weight category is to ensure good representation of subjects with diverse weights in the evaluation of safety and tolerability.

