#### **9.6 Data Analyses**

Statistical comparisons will focus on comparisons between subjects randomized to the selected *Artemisia* sp. extract and the placebo group with respect to baseline to follow-up change in: (a) a descriptive summary of adverse events, complete hematologic and biochemistry profile in blood, and measures of glucose and insulin response to glucose tolerance will be compiled for both single and multiple dose studies; (b) measurements assessing lipid metabolism, i.e. fasting lipid profile; (c) physiologic assessments of insulin action (HOMA-IR) and insulin secretion; and (d) body weight/body composition. For each outcome, the equality of the outcome means for 5011-Nutrasorb versus placebo will be tested against a two-directional alternative, controlling the type 1 error at  $\alpha = 0.05$ . The analyses will be conducted using mixed effects linear statistical

models with repeated measures to conduct analysis of variance for crossover designs. Post-hoc tests will be conducted for pairwise comparisons of extract doses and placebo employing the Tukey method for controlling the global comparison-wise significance at 0.05 level. Logarithms or other transformations will be analyzed for data seriously deviating from normality; alternatively, non-parametric analyses may be conducted.

Handling of missing data: The data will be analyzed using the procedures PROC MIXED and PROC GLIMMIX SAS (v 9.3 or later). Thus, mixed effects models for repeated measures will be employed to analyze all available data irrespective of missing or incomplete data attributable to dropouts or other phenomena. Our experience in previous studies that employed similar study designs resulted in little if any missing data. Nevertheless, in anticipation of the possibility of such we plan to conduct sensitivity analyses that compare our findings against protocol completer analyses and last observation carried forward analyses in addition to investigating characteristics of participants who fail to protocol.

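### Section 6.2 names HOMA beta-cell but prints 20 x insulin / glucose without the 3.5 offset, so a within-subject contrast on this secondary measure can change in size or direction.

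*Combined protocol and SAP*

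**What the plan says.** Section 6.2, under the calculations for insulin resistance and secretion, states "Insulin secretion will be estimated by the homeostasis assessment model of" beta-cell function, together with the insulinogenic index. It then prints the beta-cell formula as "20 \times \text{fasting insulin } (\mu\text{U/ml})] / [\text{fasting glucose } (\text{mmol/l". The denominator is fasting glucose alone. The HOMA-IR formula just above it is "fasting insulin } (\mu\text{U/ml}) \times \text{fasting glucose } (\text{mmol/l}) / 22.5", the usual form of that index.

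No other section gives a different beta-cell formula. Section 3 only names the index as a parameter: for the single-dose study, in the text below Figure 1, as "insulin response to glucose as assessed during oral glucose tolerance testing (OGTT) and with HOMA"-beta, and for the multiple-dose study as "insulin response to glucose as assessed during OGTT and with use of HOMA"-beta.

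On analysis, Section 9.2 says "among treatment comparisons will be made using within-subject data". Section 9.6 includes "physiologic assessments of insulin action (HOMA-IR) and insulin secretion" among the outcomes compared between extract and placebo, two-sided at 0.05, in mixed models for crossover data.

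**The concern.** The name and the formula do not match. HOMA beta-cell is 20 x fasting insulin / (fasting glucose - 3.5), with insulin in uU/ml and glucose in mmol/l. The printed version is a scaled insulin-to-glucose ratio. A programmer who follows 6.2 literally would report that ratio under the name of a recognised index.

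The missing term would do little harm if it only rescaled the result. It does not: subtracting 3.5 makes the index far more sensitive to small changes in fasting glucose. When glucose and insulin move in the same direction within a subject, the two versions can disagree on whether beta-cell function rose or fell. Section 6.2 singles out insulin sensitivity as the main clinical parameter on which the extract acts. A gain in sensitivity could plausibly lower fasting glucose and insulin together, which is the pattern in which the versions diverge.

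**Working it through.** **Inputs.** The printed formula comes from 6.2. The 3.5 mmol/l offset comes from the standard definition of the index named there and is not in the documents. The plan gives no expected fasting glucose, insulin or variability, so all such values below are illustrative assumptions. The plan states no numerical HOMA-beta result, so there is no figure to reproduce.

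Let I be fasting insulin (uU/ml) and G fasting glucose (mmol/l).

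- As written: W = 20 x I / G
- With the offset: O = 20 x I / (G - 3.5)
- Ratio: O / W = G / (G - 3.5)

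**Step 1: level.** At I = 8:

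| G | W | O | O / W |
|---|---|---|---|
| 4.0 | 40.0 | 320.0 | 8.00 |
| 4.5 | 35.6 | 160.0 | 4.50 |
| 5.0 | 32.0 | 106.7 | 3.33 |
| 5.5 | 29.1 | 80.0 | 2.75 |
| 6.0 | 26.7 | 64.0 | 2.40 |

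The ratio depends on glucose, so no constant converts one version into the other. Taking logarithms does not help: log O - log W = log[G / (G - 3.5)], which still varies with glucose.

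**Step 2: change within one subject.**

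| (I, G) from -> to | W | O |
|---|---|---|
| (8, 5.0) -> (8.8, 5.0) | 32.0 -> 35.2, +10.0% | 106.7 -> 117.3, +10.0% |
| (8, 5.0) -> (8, 4.8) | 32.0 -> 33.3, +4.2% | 106.7 -> 123.1, +15.4% |
| (10, 5.5) -> (9, 5.0) | 36.4 -> 36.0, -1.0% | 100.0 -> 120.0, +20.0% |
| (10, 5.0) -> (8.5, 4.7) | 40.0 -> 36.2, -9.6% | 133.3 -> 141.7, +6.25% |
| (8, 5.0) -> (8.8, 5.3) | 32.0 -> 33.2, +3.8% | 106.7 -> 97.8, -8.3% |

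At constant glucose the percentage change is the same. When only glucose moves, the size differs. When both move together, the sign can differ.

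**Step 3: how wide the reversal is.** W is unchanged when I1/I0 = G1/G0. O is unchanged when I1/I0 = (G1 - 3.5)/(G0 - 3.5). Between these two insulin ratios the versions move in opposite directions.

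- Glucose 5.5 to 5.0: 5.0/5.5 = 0.909 and 1.5/2.0 = 0.750. Any insulin fall between 9.1% and 25.0% makes W fall and O rise.
- Glucose 5.0 to 4.7: 4.7/5.0 = 0.940 and 1.2/1.5 = 0.800. The range is 6.0% to 20.0%.

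**Step 4: how often signs disagree under assumed variability.** Pairs of fasting samples from the same subject were simulated with no treatment effect, 400,000 pairs per setting. Assumptions: mean glucose 5.1 with between-subject SD 0.35 (subject levels limited to 4.2-5.6, samples floored at 3.9); median insulin 8 with between-subject log SD 0.45; within-subject glucose SD 0.15 to 0.35; within-subject insulin SD 0.15 to 0.25 on the log scale; within-subject correlation 0 or 0.4. Across the settings the two versions disagreed in sign in about 8% to 26% of pairs, and their log changes correlated 0.63 to 0.96.

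**The case against.** **The offset is outside the documents.** The figure 3.5 appears nowhere in them, and no section contradicts 6.2. That is true, and the point depends on the standard definition of the index. But that definition belongs to a method the protocol itself names, so the check sets the name against the formula and does not import a remembered study result. Consistency with the HOMA-IR constant adds little. Insulin 5 and glucose 4.5 give HOMA-IR 5 x 4.5 / 22.5 = 1.00 and an offset index of 100 (22.2 as written), but insulin 4.5 and glucose 5.0 also give HOMA-IR 1.00, with an offset index of 20 x 4.5 / 1.5 = 60. The HOMA-IR formula shows that the standard equations were intended; it does not prove the offset.

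**The term may have been lost in PDF conversion.** This cannot be excluded. Symbols lost in 3.A and 7.3 leave a visible placeholder and 6.2 shows none, but those are single characters, and a longer dropped run might leave no mark. Checking the source page therefore comes first.

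**The effect is illustrative and limited.** This stands. The reversals are single-subject examples, not the planned mean contrast, and in the simulation the signs agreed in about 74% to 92% of pairs. Sections 9.5.2 and 9.6 do not name HOMA-beta, and 9.5.2 ties secretory effects to the OGTT. The insulinogenic index also covers secretion. These facts limit the importance of the error but do not reconcile the name with the formula.

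**Conclusion.** The concern holds: as printed, 6.2 defines a quantity that is not the index it names, and the difference is not a rescaling. The versions differ by a factor from 4.5 to 2.40 across 4.5 to 6.0 mmol/l. A within-subject change can differ in size whenever glucose moves, and in sign when glucose and insulin move together within the ranges shown.

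This rests on the standard definition of HOMA beta-cell, on the printed text being complete, and, for the numerical examples, on assumed glucose and insulin values. The consequence is confined to one of two insulin-secretion measures, a secondary outcome in both studies. The primary safety outcome, HOMA-IR, the insulinogenic index, the stopping rules and the sample size are unaffected. It should be fixed, but it does not threaten the trial's main conclusions.

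**What to change.** 1. Check the source page of 6.2 for a term lost in conversion.
2. If none was lost, change the denominator in 6.2 to (fasting glucose - 3.5), glucose in mmol/l, and make the analysis program match.
3. Add one sentence on fasting glucose at or near 3.5 mmol/l, since the index is undefined at 3.5, negative below it and unstable just above it.
4. Leave transformation to the existing rule in 9.6, "Logarithms or other transformations will be analyzed for data seriously deviating from normality".

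If the plain ratio was in fact intended, renaming it as an insulin-to-glucose ratio throughout would also remove the mismatch.

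The cost is one line in 6.2, one line of code and one sentence. Fasting insulin and glucose are already collected, so the index can be recalculated without new data.

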### **6.2.1 Screening Evaluation**

These evaluations will occur to determine if the candidate is eligible for the study.

#### **Consenting Procedure**

Before any screening procedure is performed, informed consent will be obtained. There will be a single informed consent form that describes both the screening and study procedures. The study coordinator will conduct the consent process and the consent will be provided to the study subject in advance of the visit to allow time to read and address any questions. The medical investigator or Principal Investigator will also be available if any questions or clarifications are required. A copy of the consent form will be given to the subject and consent form placed in study source documents and medical records.

